11.16 Efficacy Endpoints

11.16.1 Hospitalization due to COVID-19

- Days in X = (End Date of X - Start Date of X) + 1
- Cumulative X Days = Sum of all (Days in X)

Note: X denotes Hospitalization, Intensive Care Unit (ICU) and Intubation / Mechanical Ventilations.

- Duration of COVID-19 illness before hospitalization (days) = (Initial Hospitalization Date – COVID-19 confirmation date) + 1

Note: The earliest COVID-19 confirmation date will be considered irrespective of whether or not it is prior to informed consent date.

If a subject has discontinued from the study and X is ongoing or the end date is missing, then X will be considered as ongoing at Day 14 for that subject. For cumulative X days calculation, disposition date will be considered as end date. If a subject had Ongoing Hospitalization at end of study, then end date is considered as subject's disposition date.

Note: X denotes Hospitalization, Intensive Care Unit (ICU) and Intubation / Mechanical Ventilations.

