12.9 Efficacy Analyses

All efficacy analyses will be based on FAS. Analyses will be repeated for Per-Protocol Analysis Set to check the robustness of the results (sensitivity analyses).

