12.9.2.6 Comparison of Days in Hospital, ICU and Ventilation

Cumulative number of days for Hospitalization, ICU and Intubation / Mechanical Ventilation will be compared across treatment groups using non-parametric Wilcoxon Rank Sum test. The test will be two-sided with level of significance of 5%. Descriptive summaries of cumulative number of days,

difference in treatment groups, 95% CI and unadjusted p-value will be reported. P-value will be from testing the null hypothesis that mean of cumulative days across treatment groups are same.

Reference SAS Program:

```
proc npar1way data=<data>;
  class <treatment>;
  var <days>;
run;
```

In DDP: Table 14.2.6.3 and Table 14.2.6.4

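### SAP 11.16.1 gives no day count to FAS subjects who never had an ICU or ventilator episode, so the rank-sum comparison in 12.9.2.6 is undefined for them

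*SAP*

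**What the plan says.** SAP 11.16.1 defines one spell as "Days in X = (End Date of X - Start Date of X) + 1" and the total as "Cumulative X Days = Sum of all (Days in X"). It applies both to three quantities: "X denotes Hospitalization, Intensive Care Unit (ICU) and Intubation / Mechanical Ventilations".

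Its special rules concern episodes that are still ongoing or lack an end date: "For cumulative X days calculation, disposition date will be considered as end date". Nothing covers a subject with no episode. SAP 9.1 leaves missing-data handling for efficacy to the individual sections, and neither 11.16.1 nor 12.9.2.6 supplies a rule for this case.

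SAP 12.9.2.6 then states: "Cumulative number of days for Hospitalization, ICU and Intubation / Mechanical Ventilation will be compared across treatment groups using non-parametric Wilcoxon Rank Sum test", two-sided at 5%. The reference program starts with "proc npar1way data=<data>" and passes the day variable straight to the procedure, with no zero-fill step shown. SAP 12.9 sets the population: "All efficacy analyses will be based on FAS", with a per-protocol repeat.

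SAP 12.9.2.5 reports how many subjects were ever in ICU and how many were ever ventilated, as counts and percentages, so the plan expects some subjects to have no such episode. The summary table in SAP 16.1 lists the rank-sum test for ventilator days but only descriptive summaries for hospitalization and ICU days.

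**The concern.** Days on the ventilator and ICU length of stay are secondary efficacy endpoints. Part 1 admits WHO scores 4 to 6, and score 4 is oxygen by mask or nasal, so some subjects will probably never be ventilated or enter ICU. Those are the subjects in whom a preventive effect would show.

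If they have no value, they fall out of the rank-sum test. What remains is a comparison among subjects who became ventilated or entered ICU. Treatment may influence who belongs to that group, so randomisation no longer protects the comparison. If the drug prevents the shorter courses, the treated cases that remain can look worse than the placebo cases. Two programmers working from this SAP could build different data sets and report different results.

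The same formula has a smaller defect. Each spell is counted inclusively and the spells are then added, so if one ends and the next of the same type begins on the same date, that date is counted twice.

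**Working it through.** **The plan's own figures.** No sample size or power is stated for the day-count comparisons. The stated figures concern the primary endpoint (SAP 4.2: 20% vs 5%, one-sided alpha 0.2, N=54, about 80% power, minimum observed difference 8.4%). They reproduce with the normal-approximation test without continuity correction: 27 per arm, power 80.1%, minimum difference 8.36%. This point does not affect them.

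**Step 1: the rule for a subject with no episode.** The spell formula needs a start date and an end date, and a never-ventilated subject has neither. The ongoing and missing-end-date rules do not apply, because nothing was started. If the total is built from episode records, such a subject has no record and hence no value. Omitting missing values is standard behaviour of the rank-sum procedure, not something the SAP states.

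**Step 2: how many subjects the test would use.** Inputs: 30 per arm (Protocol 7.1, Part 1). Ever-ventilated rates are assumptions. The first pair borrows the 20%/5% planning rates, which are Day 14 composite rates and not ever-ventilated rates. If no-episode subjects are dropped, the expected number analysed is 30 × (placebo rate + active rate):
- 20% vs 5%: 30 × 0.25 = 7.5 of 60
- 30% vs 10%: 30 × 0.40 = 12 of 60
- 40% vs 15%: 30 × 0.55 = 16.5 of 60

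At a 5% rate, the chance that the active arm has no ventilated subject is 0.95^30 = 0.215. In about one trial in five no comparison would be possible.

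**Step 3: effect on the test.** Simulation with 30 per arm, a two-sided 5% rank-sum test, and the same duration distribution among the ventilated in both arms. It was run with lognormal durations (median 10 days, log-SD 0.7; 3,000 trials per scenario) and with gamma durations (mean about 10 days; 4,000 trials).

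| Assumed ever-ventilated, placebo vs active | Rejection, no-episode = 0 | Rejection, no-episode dropped |
|---|---|---|
| 20% vs 5% | 41% (gamma 42%) | 0.7% (gamma 0.7%) |
| 30% vs 10% | 48% (gamma 50%) | 2.6% (gamma 2.6%) |
| 40% vs 15% | 57% (gamma 59%) | 3.9% (gamma 4.0%) |

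With no effect (20% in both arms, gamma), rejection is 5.0% with zeros and 3.5% if dropped.

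**Step 4: what the contrast measures.** A chi-square test on ever-ventilated, yes or no, rejects in about 45%, 51% and 59% of trials in the same three scenarios, close to the zero-coded rank-sum test. The zero-coded result is therefore almost entirely the difference in ever being ventilated. The dropped version has no duration difference to find, so its rejection rate is a null rate, lowered further by small or empty arms.

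**Step 5: direction can reverse (constructed example).** Placebo: 6 of 30 ventilated, for 4, 6, 10, 14, 18 and 20 days (sum 72). Active: 2 of 30, for 18 and 20 days (sum 38).
- With zeros: 72/30 = 2.4 vs 38/30 = 1.3 days, favouring active.
- Ventilated only: 72/6 = 12 vs 38/2 = 19 days, favouring placebo.

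**Step 6: shared dates.** Stays on Days 1-5 and 5-10 give (5 − 1 + 1) + (10 − 5 + 1) = 5 + 6 = 11 days for 10 calendar dates, or +1 per shared date. Adding one day to a random 30% of ventilated subjects in each arm, zeros kept, moved rank-sum rejection by about 0.1 percentage point or less.

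**The case against.** A reader might infer that the SAP excludes subjects with no episode and that they are the majority. The documents support neither inference. No sentence excludes them. SAP 12.9 and the table in 16.1 place these analyses on the FAS, which points towards including everyone. A sum over no spells can reasonably be read as 0, and the reference program is a skeleton that does not show how the day variable is built. On numbers, the 20%/5% rates are not ever-ventilated rates, WHO 6 can include intubated subjects, and no ICU rate is given anywhere. All of this stands: the SAP is undefined here, not committed to exclusion.

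A preventive effect would also show elsewhere. SAP 12.9.2.5 reports ever-ventilated and ever-ICU counts by arm, and 12.9.2.3 compares the proportions alive and free of support on five days. The first is descriptive and the second a composite, so they soften the consequence without defining the day count.

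The power contrast would mislead if read as lost power to detect shorter ventilation. Step 4 shows that it is not that.

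A bare zero rule is also incomplete, since a subject who dies without ventilation or ICU would receive the best rank. This is correct, and the fix has to deal with it.

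The double count needs two same-type spells sharing a date, and the documents give no frequency. It is a minor note.

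These are secondary tests with unadjusted p-values, which SAP 8.2 already says to interpret with caution.

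**Conclusion.** The gap is real and limited. SAP 11.16.1 gives no value for FAS subjects without an ICU or ventilator episode, and 12.9.2.6 tests that variable with no rule to fill it. If the values are left missing, the test becomes a comparison within a subset formed after randomisation, contrary to 12.9.

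The rejection rates of about 41-57% with zeros against about 1-4% without rest on three things: the assumed ever-ventilated rates, equal durations in both arms, and no-episode subjects actually being left missing. They show that the undefined choice can decide the result. They do not predict this trial. The reversal in Step 5 shows what is possible and was not estimated.

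Hospital days are outside the no-episode gap because every subject is hospitalized. The SAP covers the WHO 4-6 population; Part 2 subjects are all intubated at entry and are only described (Protocol 11.1). The primary analysis and N=54 are untouched. The shared-date double count is exact, at +1 day per shared date, but small. The disagreement between 16.1 and 12.9.2.6 over testing ICU days also needs settling. The point should be addressed before the analysis is run.

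**What to change.** In SAP 11.16.1:
- State that FAS subjects with no ICU episode, or no ventilator episode, have 0 days for that quantity and stay in the 12.9.2.6 comparison.
- State how deaths are ranked, so that death without ventilation or ICU does not score as the best outcome.
- Define Cumulative X Days as the number of distinct calendar dates on which X was in place, in place of the sum of inclusive spells.

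In SAP 16.1 and 12.9.2.6, reconcile whether ICU days are tested or only described.

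The cost is a few sentences and a small programming change, with no new data. The ranking of deaths is the one item that needs a decision, and it should be made before unblinding.

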11.16.2 URB-65 Score

The score is an acronym for each of the risk factors measured. Each risk factor scores one point, for a maximum score of 5:

- Confusion of new onset (defined by the Abbreviated Mental Test Score [see Appendix B] of 8 or less [2 or more incorrect answers])
- Blood Urea nitrogen greater than 7 mmol/l (19 mg/dL)
- Respiratory rate of 30 breaths per minute or greater
- Blood pressure less than 90 mmHg systolic or diastolic blood pressure 60 mmHg or less
- Age 65 or older

11.16.3 Abbreviated Mental Health Score

The questions are put to the patient. Each question correctly answered scores one point. A score of 8 or less suggests cognitive impairment at the time of testing, although further and more formal tests are necessary to confirm a diagnosis of dementia, delirium or other causes of cognitive impairment.

- What is your age? (1 point)
- What is the time to the nearest hour? (1 point)
- Give the patient an address and ask him or her to repeat it at the end of the test. (1 point)

- *e.g. 42 West Street*
- *What is the year? (1 point)*
- *What is the name of the office or doctor you are seeing today? (1 point)*
- *Can the patient recognize two persons (the doctor, nurse, home help, etc.)? (1 point)*
- *What is your date of birth? (day and month sufficient) (1 point)*
- *In what year was the 9-11 terrorist attack? (1 point) (other dates can be used, with a preference for dates sometime in the past)*
- *Name the present president of the USA. (1 point)*
- *Count backwards from 10 down to 1. (1 point)*

11.16.4 WHO Severity Scores

The 9-point WHO classification scheme from 0 to 8 for COVID-19 pneumonia will be applied to grade the severity of illness as follows:

- *8 - Death*
- *7 - Mechanical ventilation or extracorporeal membrane oxygenation (ECMO), vasopressor support, dialysis/renal replacement therapy (RRT)*
- *6 - Intubation with mechanical ventilation, a mask with a reservoir or oxygen with high-flow nasal goggles.*
- *5 - Noninvasive ventilation (continuous positive airway pressure [CPAP] or bilevel positive airway pressure [BiPAP]) or high-flow oxygen*
- *4 - Oxygen by mask or nasal*
- *3 - Hospitalized with no oxygen therapy*
- *2 - Limitation of activity*
- *1 - Infected without limitations*
- *0 - No clinical or virologic evidence of COVID-19 infection*

Higher WHO Severity Score indicates worse conditions.

11.16.5 Subjects Discharged

Subjects will be considered as discharged at all visits after the discharge date. If there is more than one hospitalization for a subject, then the latest hospitalization will be considered.

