### 5.2.2. Secondary Endpoints

- Safety and tolerability
  - Incidence, causality, and severity of AEs (graded according to the National Cancer Institute [NCI] Common Terminology Criteria for Adverse Events [CTCAE] version 5.0) in rhu-pGSN vs placebo groups
  - Frequencies of new or worsening clinically significant laboratory abnormalities in rhu-pGSN vs placebo groups
  - Mortality rate irrespective of cause at Days 28 and 90
- Efficacy
  - Daily change in 9-point WHO severity score through at least Day 14 (including after discharge, where feasible)
  - All-cause mortality at Days 28 and 90; time to death (Kaplan-Meier survival analysis)
  - Proportion of subjects alive on Days 7, 14, 28, 60, and 90 without:
    - Ongoing use of vasopressors
    - Ongoing intubation/mechanical ventilation
    - Ongoing residence in an ICU
    - New ongoing need for dialysis/renal replacement therapy (RRT)
  - Proportion of subjects discharged to home or immediate prior residence by Day 28
  - Days on the ventilator
  - Length of stay (LOS) in hospital and in ICU (days)
  - Re-admission to an acute-care hospital up to Day 90
- PK
  - PK for rhu-pGSN including maximum concentration ( $C_{max}$ ), time to maximum concentration ( $T_{max}$ ), terminal half-life ( $T_{1/2}$ ), area under the curve from time zero to 8 hours ( $AUC_{0-8}$ ), area under the curve from time 0 to infinity ( $AUC_{inf}$ ) for Dose #1 within 15 minutes predose, and at 1 ( $\pm 15$  min), 2 ( $\pm 15$  min), 6 ( $\pm 30$  min), and 12 ( $\pm 30$  min) hours after end of administration (but prior to Dose #2); for Dose #3 within 15 minutes predose, and at 1 ( $\pm 15$  min), 2 ( $\pm 15$  min), 6 ( $\pm 30$  min), 12 ( $\pm 30$  min) and 24 ( $\pm 30$  min) hours after the end of administration (participants refusing these blood samplings can enter and remain in the trial).
- Immunogenicity
  - Presence of anti-pGSN antibodies on Days 1 (predose), 28, and 90

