11.17 Criterion Flags

- Subjects who are alive at the given timepoints with the below mentioned criteria will be flagged as 'Y' in the analysis datasets. All subjects within Per-Protocol and FAS will be flagged irrespective of their disposition status. Any ambiguity in subject status will be considered as failure and flagged as 'N'.

Criterion Flag	Criteria	Other Criteria
Flag 01	Alive on Day 14	Without the following (end date prior to day 14): 
 • Ongoing use of vasopressors • Ongoing intubation/mechanical ventilation

		
 • New ongoing need for dialysis/renal replacement therapy (RRT)
Flag 02	Alive on Day 7	Without the following (end date prior to day X):
Flag 03	Alive on Day 14	
 • Ongoing use of vasopressors
Flag 04	Alive on Day 28	
 • Ongoing intubation/mechanical ventilation
Flag 05	Alive on Day 60	
 • Ongoing residence in an ICU
Flag 06	Alive on Day 90	
 • New ongoing need for dialysis/renal replacement therapy (RRT)

- Subjects who were discharged will be flagged 'Y' in the analysis datasets based on the following criteria:

Criterion Flag	Criteria
Flag 07	Discharged on Day 14
Flag 08	Discharged on Day 28
Flag 09	Discharged on Day 60
Flag 10	Discharged on Day 90

If a subject does not meet the given criteria, they will be flagged as 'N'. All subjects within Per-Protocol and FAS will be flagged irrespective of their disposition status.

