12.9.2.4 Proportion of Subjects Discharged

Number and percentage of subjects who were discharged on or before Days 14, 28, 60 and 90 will be summarized by treatment group. Proportions within each treatment group along with 95% CI will be

provided using Clopper-Pearson method for each visit. Risk Differences between treatment groups and p-value from testing the null hypothesis that there are no differences between treatment groups will be reported based on Fisher's Exact test. The summary will be based on FAS and repeated for Per-Protocol Analysis Set.

Reference SAS Program:

```
/* 95% CI for binomial (exact Clopper-Pearson) */

proc freq Data=XXX alpha=0.05;
  by treatment;
  tables flag/binomial(level='1' exact);
run;

/* 95% CI for risk difference and p-value from Fisher's test */

proc freq Data=XXX alpha=0.05;
  tables treatment*flag/riskdiff(cl=exact);
  exact riskdiff fisher;
run;
```

In DDP: Tables 14.2.5.1 and 14.2.5.2 and Listing 16.2.6.2

12.9.2.5 Hospitalization due to COVID 19

Number and percentage of subjects re-admitted to an acute-care hospital and subjects who are ongoing hospitalization at Day 14 will be summarized. Descriptive summaries for Duration of COVID-19 illness before hospitalization and cumulative number of hospitalization days will also be summarized.

Number and percentage of subjects who have been to the ICU and subjects who are still in ICU at End of Study will be summarized. Descriptive summary for cumulative number of ICU days will also be summarized.

Number and percentage of subjects who had Intubation / Mechanical Ventilations and subjects who are still in Intubation / Mechanical Ventilations at End of Study will be summarized. Descriptive summary for cumulative number of Intubation / Mechanical Ventilations days will also be summarized.

All summaries will be based on FAS and per-protocol analysis sets. Percentages will be based on the corresponding analysis sets.

In DDP: Table 14.2.6.1 and Table 14.2.6.2

Hospitalization, ICU and Intubation / Mechanical Ventilations will be listed by subject.

In DDP: Listings 16.2.6.2, 16.2.6.3, and 16.2.6.4

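### The SAP's working definition of the Day 28 discharge endpoint omits the required destination, and read literally its latest-hospitalization rule lets a readmission after Day 28 cancel a Day 28 discharge

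*SAP*

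**What the plan says.** Protocol 5.2.2 lists, among the secondary efficacy endpoints, "Proportion of subjects discharged to home or immediate prior residence by Day 28". SAP 7.2.2 repeats it with the destination intact. A separate secondary endpoint in the same protocol section is "Re-admission to an acute-care hospital up to Day 90".

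Three places in the SAP turn the discharge endpoint into data and a test:

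- SAP 11.16.5 gives the status rule: "Subjects will be considered as discharged at all visits after the discharge date". For repeat stays it adds: "If there is more than one hospitalization for a subject, then the latest hospitalization will be considered".
- SAP 11.17 defines Flag 08 only as "Discharged on Day 28". Subjects who do not meet a criterion are flagged N and stay in the denominator.
- SAP 12.9.2.4 summarises the "Number and percentage of subjects who were discharged on or before Days 14, 28, 60 and 90", with Clopper-Pearson intervals, risk differences and Fisher's exact test.

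SAP section 13 lists two departures from the protocol: the visits used for the WHO score, and the dropped external-control comparison. Neither concerns discharge.

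**The concern.** There are three separate gaps.

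1. **Destination.** None of the three operational places says where the subject must be discharged to. A programmer working from them would score a discharge to, say, a long-term care facility as a success. The protocol scores it as a failure unless the subject lived there before.
2. **Later events.** The repeat-stay rule is written per subject, not per assessment day. Readmissions are followed to Day 90, so second stays starting after Day 28 are expected. On the literal wording they change a result that was already fixed at Day 28.
3. **Boundary.** A discharge on Day 28 itself is N under 11.16.5 and Y under 12.9.2.4.

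At stake is whether the reported proportion, interval and Fisher test describe the endpoint the protocol names, and whether two programmers would produce the same table from the same data.

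**Working it through.** The documents give no expected rate, sample size or power for this endpoint, so there is no planned figure to reproduce. The check compares the texts and then applies the rules to test histories.

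**Destination, text against text**

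| Place | Destination stated? | Time rule |
|---|---|---|
| Protocol 5.2.2 | yes | by Day 28 |
| SAP 7.2.2 | yes | by Day 28 |
| SAP 11.16.5 | no | visits after the discharge date |
| SAP 11.17, Flag 08 | no | on Day 28 |
| SAP 12.9.2.4 | no | on or before Day 28 |
| SAP 13 | no departure declared | none |

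**Repeat stays and boundary, Day 28 flag**

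- Rule L (11.16.5 read literally): Y if Day 28 is later than the discharge date of the subject's latest stay of all.
- Rule A: the same, but using the latest stay begun on or before Day 28.
- Rule F: Y if the first discharge falls on or before Day 28.

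| History | L | A | F |
|---|---|---|---|
| Discharged Day 20, no readmission | Y | Y | Y |
| Discharged Day 20, readmitted Days 40-50 | N | Y | Y |
| Discharged Day 20, readmitted Day 40, ongoing | N | Y | Y |
| Discharged Day 10, readmitted Days 20-25 | Y | Y | Y |
| Discharged Day 10, readmitted Days 26-35 | N | N | Y |
| Discharged on Day 28 | N | N | Y |

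Three results follow.

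- L and A differ at Day 28 only when the readmission begins after Day 28. In the second row, L also gives N at Day 28 but Y at Days 60 and 90, although the subject was already out of hospital on Day 28.
- In the fifth row the subject is back in hospital on Day 28. A and F disagree, and the protocol wording does not settle which is meant.
- In the last row the disagreement comes only from the boundary. Rule A with an on-or-before boundary would give Y.

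**Size**

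Protocol 7.1 plans 30 subjects per arm in Part 1. One reclassified subject moves an arm by 1/30 = 3.3 percentage points.

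The number of such subjects cannot be taken from the documents. As an illustration only, assume 24 of 30 in an arm are discharged by Day 28 (24/30 = 80%) and a share r of them is readmitted after Day 28. Under rule L the expected proportion is 24 × (1 − r)/30:

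- r = 5%: 22.8/30 = 76%
- r = 10%: 21.6/30 = 72%
- r = 20%: 19.2/30 = 64%

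Both the 24 of 30 and the values of r are assumptions.

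**Direction**

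Dropping the destination can only raise the proportion. Compared with rule A, rule L can only lower it. The net direction is unknown.

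**The case against.** The strongest reply is that 11.16.5 is a visit-level status rule, so its latest hospitalization may mean the latest as of each visit. The on-or-before wording of 12.9.2.4 fits that reading, and under it nothing after Day 28 can change the Day 28 flag. This is a fair reading, but 11.16.5 does not say it. What stands is that the cancellation follows from the literal wording and is not certain to be programmed.

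Several stronger conclusions are tempting, and the documents do not support them.

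- *The SAP has abandoned the protocol endpoint.* It has not: 7.2.2 keeps the destination. The SAP is inconsistent with itself. The Data Display Plan and the eCRF, which might carry the destination, are not available for review.
- *Every transfer would count as a discharge.* A hospital-to-hospital transfer may be recorded as a second hospitalization, and the latest-stay rule would then use the final discharge. Only discharge to a facility that is neither a hospital nor the subject's residence clearly slips through.
- *The treatment comparison is biased.* The arithmetic shows a shift in the level of an arm. Similar misclassification in both arms would leave much of the comparison intact. Distortion of the difference requires the affected share to differ by arm, and the documents give no rates.
- *Readmission is hidden inside discharge.* SAP 12.9.2.5 already summarises readmissions separately.
- *The first stay is the right basis.* That would score a subject back in hospital on Day 28 as a success. Sustained discharge is equally defensible.

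The weight is also limited. SAP 8.2 asks for caution with secondary tests, and hospitalizations are listed by subject, so dates could be re-derived.

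**Conclusion.** The point holds in a bounded form. The missing destination is plain on the text and does not depend on how the repeat-stay rule is read: the operational SAP defines a broader endpoint than the protocol and SAP 7.2.2, with no declared change. The boundary conflict is also plain, but it touches only discharges on the assessment day itself. Cancellation by a later readmission rests on the literal reading of 11.16.5.

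Each subject reclassified by that rule is worth 3.3 points in a 30-subject arm. How many there would be is unknown, and so is the net direction across the faults. This is a secondary endpoint only. The primary flag (Flag 01) rests on survival and organ support at Day 14 and does not use discharge status.

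**What to change.** - Add the destination condition to Flag 08 and to 12.9.2.4. If destination was not collected, declare the departure in section 13 and label the table as discharge to any destination.
- Restrict the repeat-stay rule in 11.16.5 to hospitalizations begun on or before Day X.
- State explicitly how a readmission before Day X is handled, in particular for a subject who is back in hospital on Day X.
- Use an on-or-before boundary in 11.16.5, 11.17 and 12.9.2.4.

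The cost is a few sentences in the SAP and one derivation, provided that destination is on the eCRF, which the documents do not show. If it is not, adding it late may not be feasible, and the declaration in section 13 is the realistic course. The date and boundary changes need only the hospitalization dates already collected.
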